9.2.2. Exclusion criteria

There are no exclusion criteria for this study.

[figure not shown]
9.2.3. Index Date and Follow-Up

The index date will be the date of the first filled prescription/dispensing of somatrogon or once daily somatropin as recorded in the data sources. The patients will be followed from the index date to whichever of the following that occurs first:

- Primary or secondary safety event of interest (follow-up time will be from the index date to the date of the event, at which the patient will be censored for that particular event of interest. Follow-up will continue for the other safety events of interest)
- Death
- Lost to follow-up (eg, via migration out of the country as documented in the data source(s)), or
- End of the study follow-up

The study will span a 10-year study period, throughout which patients can accrue and will be evaluated in 2 stages. First, patients will be accrued within the first 5 years and followed for a minimum of 5 and up to 10 years to evaluate long-term safety events of interest, Figure 1. Second, in sensitivity analyses, all patients that accrue after the 5-year mark, and therefore, with less than 5 years of follow-up, will be analyzed both separately and together with the study population. (Section 9.7.2.4)

Figure 1. Patients Inclusion and Follow-up

Inclusion of patients prescribed/dispensed with at least 1 dose of somatrogon or once daily somatropin

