8. RESEARCH QUESTION AND OBJECTIVES

The primary research question for this study is: What is the long-term safety in paediatric patients treated with somatrogon in real-world routine clinical practice?

Primary Objective:

Estimate the incidence rates of neoplasms, and diabetes mellitus type 2, the primary safety events of interest in paediatric patients treated with somatrogon, and paediatric patients treated with once daily somatropin, in the course of routine clinical care.

Secondary Objectives:

- a) Estimate the incidence rates of clinical endpoints related to immunogenicity, medication errors, the secondary safety events of interest, in paediatric patients treated with somatrogon, and paediatric patients treated with once daily somatropin, in the course of routine clinical care.
- b) Evaluate long-term efficacy by measuring IGF-1 levels, and height in paediatric patients treated with somatrogon, and paediatric patients treated with once daily somatropin, in the course of routine clinical care.
- c) Estimate the hazard ratios of neoplasms, and diabetes mellitus type 2, the primary safety events of interest between paediatric patients treated with somatrogon, and paediatric patients treated with once daily somatropin, in the course of routine clinical care.
- d) Estimate the hazard ratios of the clinical endpoints related to immunogenicity, the secondary safety events of interest, between paediatric patients treated with somatrogon, and paediatric patients treated with once daily somatropin, in the course of routine clinical care.

The safety events of interest noted above, are based on the current understanding of the important potential risks associated with somatrogon. However, other endpoints may be added as understanding of the safety profile of somatrogon evolves and feasibility of their assessment permits.

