9.3. Variables

Operational definitions of the following variables will be described in the statistical analysis plan (SAP).

Exposure:

- First filled Somatrogon prescription/dispensing following registration of the product in EU and UK.
- For the internal comparator, first filled somatropin prescription during the same study period as somatrogon patients.

As noted above, operational definitions of exposure will be specified in the SAP (eg, if feasible and subject to sample size, by: somatrogon use, those who switch between somatrogon and somatropin, or somatropin use).

Outcomes

The following are the safety events of interest:

Primary-

- neoplasms
- diabetes mellitus type 2

Secondary-

• immunogenicity

Where feasible, to evaluate immunogenicity within the respective databases, the following clinical endpoints related to immunogenicity will be captured:

- o Bronchospasm
- Allergic conjunctivitis
- o Allergic dermatitis
- Atopic dermatitis
- Eyelid oedema
- Henoch-Schonlein purpura
- Hypersensitivity
- o Rash
- o Allergic rhinitis
- Swelling face
- Swelling of eyelid
- Urticaria
- Medication errors

Where feasible, to evaluate medication errors for somatrogon within the respective databases, utilizing prescription information and weight

measurements, the following endpoints related to medication errors will be captured:

- Underdosing defined as a:
 - 50% decrease in dose for a single administration (or, dispensing that is <0.33 mg/kg body weight)
 - o Missing a dose within the course of 2 weeks
- Overdosing defined as:
 - o 50% increase in dose for a single administration (or, dispensing that is >0.99 mg/kg body weight)
 - O An extra dose administration within 4 days of the last dose

(The recommended dose for somatrogon is 0.66 mg per kilogram of body weight via a single weekly injection, adjusted by the doctor if necessary.)

For somatropin, the recommended dose in mg per kilogram of body weight via a daily injection, will be manufacturer dependent. Analogous to somatrogon, underdosing and overdosing will be defined as a 50% decrease and increase in dose for a single administration, respectively.

• Long-term efficacy

Where feasible, to evaluate long-term efficacy within the Swedish Growth Hormone Registry database, the following endpoints related to long-term efficacy will be captured:

- o IGF-1 levels
- Height (height velocity (HV), height standard deviation score (SDS), change in height SDS, and final height).

Covariates:

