9.7. Data analysis

The primary analysis will be descriptive and all eligible patients during the study period will be included, with no upper limit on the sample size. Due to database heterogeneity, analyses will be conducted separately by data source and data will not be pooled.

Baseline demographic and clinical characteristics for each treatment group will be described. For all the safety events of interest and efficacy measurements of interest, descriptive statistics, counts and proportions, crude incidence rates (ie, number of events per person years) and age/sex standardized incidence rates with associated two-sided 95% confidence intervals will be calculated as appropriate.

The summary of event rates will be based on survival analysis of time to first event based on an index date defined for each treatment group with appropriate censoring rules applied for those who do not experience an event by end of follow-up period including those who die, those who are lost to follow-up (eg, via migration out of the country as documented in the data source), or end of study period. Rates will be expressed as events/1,000 person-years of follow-up.

The primary objective of the study is active surveillance (to estimate the incidence rates of neoplasms, and diabetes mellitus type 2, the primary safety events of interest in paediatric patients treated with somatrogon, and paediatric patients treated with once daily somatropin, in the course of routine clinical care). Conducting quantitative, confounding-controlled comparative analyses will depend on having a sufficient sample size. The feasibility of more formal comparative analyses to evaluate safety events of interest that adequately adjust for potential confounders will be assessed in the interim reports, and at study end will be based on statistical power as described below. Since the size of the once daily somatropin-treated comparator group is expected to be a magnitude larger than the somatrogon-treated group,

statistical power will be limited by the uptake of somatrogon (which is difficult to estimate a priori).

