- Given the potential latency for neoplasm development, the study may underestimate its occurrence during the 10-year study period. Moreover, as indication specific data elements are not available in SNDS, THIN, Swedish national data, it is possible that GH treatment was indicated for patients as a direct result of a neoplasm (eg, removal of an intracranial tumor led to GHD, GH treatment is given, but there is a neoplasm recurrence; Boguszewski et al 2021).
- Exposure to more than one recombinant GH treatment during study follow-up may occur. In the comparative analysis, censoring follow-up time after a switch, or parameterizing treatment exposure as a time-varying covariate, serves to in part to account for this. However, these methods assume that patients who switch are prognostically similar to patients who do not switch, which may not necessarily be true.

- Medication errors resulting from the administration or consumption of treatment by the wrong patient, or at the wrong time, or at the wrong dosage strength, will not be captured in this study. Moreover, medication errors as currently defined will not account for titration used to maintain IGF-1 levels. For example, patients may have had a scheduled dose decrease of 15% due to IGF-1 SDS>2 or adverse events. If a patient had a dose prescribed that required a 15% decrease in dose, this would be captured as a medication error when in fact it is not. Lastly, sufficient accuracy of estimating medication error (for Sweden, Spain LPD, and UK THIN) at a single dose or at a weekly level will be limited, because it is a function of data availability and timing of both weight measures and GH treatment. For instance, in the Swedish GH registry the provider has to report missing doses every 6 months; medication errors are captured as an aggregate measure at the 3–6-month level.
- Broad definitions of immunogenicity clinical endpoints, such as hypersensitivity, may overestimate their occurrence and does not account for multiple symptoms stemming from one unifying, underlying condition (eg, hypersensitivity and allergic conjunctivitis, as it relates to atopic dermatitis).

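### Medication errors can recur, but the first-event rule gives only the incidence of a first error, which falls below the overall error rate if children differ in error-proneness

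*Protocol*

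**What the plan says.** Secondary objective (a) in Protocol section 8 is to "Estimate the incidence rates of clinical endpoints related to immunogenicity, medication errors, the secondary safety events of interest", for somatrogon and for once daily somatropin.

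Section 9.2.3 lists what ends follow-up. The first item reads "Primary or secondary safety event of interest (follow-up time will be from the index date to the date of the event", and continues "at which the patient will be censored for that particular event of interest"; follow-up for the other safety events goes on. Section 9.7 then states: "The summary of event rates will be based on survival analysis of time to first event". It also promises counts, proportions and "crude incidence rates (ie, number of events per person years") for all safety events, as appropriate. Neither section sets a different rule for medication errors.

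Section 9.3 defines errors per single administration or dispensing (dose too low or too high), per extra administration within a few days, and by "Missing a dose within the course of 2 weeks". Section 9.9 notes that in the Swedish growth hormone registry "medication errors are captured as an aggregate measure at the" 3 to 6 month level. Section 9.7 rules out a comparative analysis of medication errors, so the descriptive summaries are the only output for this part of objective (a).

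**The concern.** Ending the clock at the first event suits a neoplasm or a first diagnosis of type 2 diabetes. It suits a dosing error poorly. A child whose first error comes in month two contributes one event and two months, whether no further errors or twenty follow.

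This has two consequences. Repeat errors are lost, which costs information. And if some children err more often than others, they leave the risk set first, so the remaining person-time comes increasingly from children who seldom err. The events-per-person-years figure then drops below the average error rate and depends on how long the children are followed. A reader of a safety report may take that figure as how often errors happen in practice. Section 9.9 lists several limits on medication errors but not this one.

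**Working it through.** The protocol states no medication-error rate, sample size or power, so there is no figure to reproduce. The check compares the first-event rate with the all-errors rate under a standard model.

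**Inputs from the protocol**
- Follow-up of 5 to 10 years (9.2.3).
- Constant accrual and 5% annual loss in both groups (9.5, table assumptions).

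With administrative follow-up uniform on 5 to 10 years and 5% annual loss, mean follow-up is 6.19 years; T = 6.2 is used below.

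**Inputs assumed (not in the protocol)**
- Mean error rate L per child-year: 0.05, 0.2, 0.6.
- Between-child variation: each child's rate is L times a gamma variable with mean 1 and variance v, from 0 (all alike) to 2.

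**Formulas**
- Probability of at least one error by T: P = 1 − (1 + vLT)^(−1/v).
- Mean time at risk: A = ∫₀ᵀ (1 + vLt)^(−1/v) dt. For v = 1 this is ln(1 + LT)/L; for v = 2 it is [√(1 + 2LT) − 1]/L.
- First-event rate = P/A, compared with L.

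**All children alike (v → 0)**
The first-event rate equals L, so there is no bias. Information is still lost: at L = 0.6, LT = 3.72 and first errors are (1 − e^(−3.72))/3.72 = 26% of all errors, so 74% are not counted.

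**Children differ, T = 6.2**

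| L | v | P | A (years) | P/A | Shortfall against L |
|---|---|---|---|---|---|
| 0.05 | 0.5 | 0.250 | 5.37 | 0.047 | 7% |
| 0.05 | 1 | 0.237 | 5.40 | 0.044 | 12% |
| 0.2 | 1 | 0.554 | 4.03 | 0.137 | 31% |
| 0.2 | 2 | 0.464 | 4.33 | 0.107 | 46% |
| 0.6 | 1 | 0.788 | 2.59 | 0.305 | 49% |
| 0.6 | 2 | 0.656 | 3.18 | 0.207 | 66% |

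For example, at L = 0.6 and v = 1: P = 3.72/4.72 = 0.788; A = ln(4.72)/0.6 = 2.59; P/A = 0.305; 1 − 0.305/0.6 = 49%.

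**Spread-out follow-up**
Replacing the fixed 6.2 years by the full follow-up distribution (uniform 5 to 10 years, 5% annual loss) gives ratios of 0.925 and 0.864 at L = 0.05 (v = 0.5 and 1), shortfalls of 7.5% and 13.6%. Across both versions the shortfall for rare errors is therefore about 7-14%. A simulation of 400,000 children at L = 1 gives first-event rates of 0.998 (v = 0), 0.437 (v = 1) and 0.271 (v = 2), in line with the integrals.

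**Shorter treated time**
Errors occur only on treatment, and 6.2 years is total follow-up. With an assumed 3 treated years and v = 1, the shortfall is 20% at L = 0.2 (0.375/2.35 = 0.160) and 38% at L = 0.6 (0.643/1.716 = 0.375).

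**The case against.** - **A first-event rate is a legitimate incidence measure.** This stands. The figure is not wrong for what it measures; it answers a different question from how often errors occur, and the protocol does not say that only first errors are meant.
- **The clock may run per endpoint.** Section 9.2.3 censors only for the particular event, and 9.3 lists several error endpoints. A first underdose need not end follow-up for overdosing. A reader might infer one composite clock that stops at any error; the text does not say so. The per-endpoint reading softens the point but does not remove it, because each endpoint can itself recur.
- **Counts and proportions are also planned.** True, so the share of children with any error is already covered. Whether counts include repeats is not stated, and 9.2.3 still stops the clock.
- **The SAP may change this.** Section 9.3 leaves operational definitions to the SAP, and 9.7 lets it modify plans. But the first-event rule is stated in the protocol without exception; it is not a detail left open.
- **Immunogenicity endpoints can recur too.** They can. Objective (d), however, plans hazard ratios for them, for which time to first event is natural. Medication errors have no such analysis.
- **Counting every error may be less reliable.** This has force. Section 9.9 admits that injected dose is unknown, that titration may be read as error, and that Swedish data are aggregated. A naive count would score one sustained out-of-range prescription at every refill. The fix has to deal with this.

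**Conclusion.** The concern holds in a limited form. As written, sections 9.2.3 and 9.7 yield the incidence of a first medication error. That figure discards repeat errors and later person-time, and lies below the overall error rate whenever children differ in error-proneness.

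How far below cannot be read from the protocol. The shortfalls worked out above run from nil to 66%, and every one of them rests on an assumed error rate and an assumed variation between children; shorter treated time makes them smaller. A reader might infer that the reported rate is bound to be far too low. The documents do not support that: it is true only if errors are not rare and children differ materially.

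A reader might also infer that the two treatment groups will be followed for different lengths of time and so show different rates for the same error frequency. The protocol does not support this either: section 9.1 accrues both groups over the same period, section 9.5 assumes constant accrual and 5% annual loss in each, and no comparative analysis of errors is planned.

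The point concerns one descriptive secondary outcome and leaves the primary objective untouched. It deserves correction because the descriptive summaries are all that will be reported on errors and the change is cheap.

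**What to change.** In sections 9.2.3 and 9.7, exempt medication errors from censoring at first event. For each error endpoint:

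- Report all distinct error episodes over assessable on-treatment person-time, and per 100 assessable dispensings or prescriptions. In the Swedish growth hormone registry, use the reporting period as the unit, since errors are aggregated there.
- Count a sustained run of the same out-of-range prescription as one episode.
- Give a 95% confidence interval that allows for clustering within child (robust Poisson or negative binomial).
- Keep the first-event rate and the proportion of children with at least one error alongside, labelled as such.

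Leave time to first event in place for neoplasms, diabetes and the immunogenicity endpoints.

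The cost is a short addition to each of the two sections, an episode rule to be defined (the SAP can hold it), and slightly more programming. No new data are needed. The limits on dose measurement in section 9.9 remain and should be stated with the result.

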9.3. Variables

Operational definitions of the following variables will be described in the statistical analysis plan (SAP).

Exposure:

- First filled Somatrogon prescription/dispensing following registration of the product in EU and UK.
- For the internal comparator, first filled somatropin prescription during the same study period as somatrogon patients.

As noted above, operational definitions of exposure will be specified in the SAP (eg, if feasible and subject to sample size, by: somatrogon use, those who switch between somatrogon and somatropin, or somatropin use).

Outcomes

The following are the safety events of interest:

Primary-

- neoplasms
- diabetes mellitus type 2

Secondary-

• immunogenicity

Where feasible, to evaluate immunogenicity within the respective databases, the following clinical endpoints related to immunogenicity will be captured:

- o Bronchospasm
- Allergic conjunctivitis
- o Allergic dermatitis
- Atopic dermatitis
- Eyelid oedema
- Henoch-Schonlein purpura
- Hypersensitivity
- o Rash
- o Allergic rhinitis
- Swelling face
- Swelling of eyelid
- Urticaria
- Medication errors

Where feasible, to evaluate medication errors for somatrogon within the respective databases, utilizing prescription information and weight

measurements, the following endpoints related to medication errors will be captured:

- Underdosing defined as a:
 - 50% decrease in dose for a single administration (or, dispensing that is <0.33 mg/kg body weight)
 - o Missing a dose within the course of 2 weeks
- Overdosing defined as:
 - o 50% increase in dose for a single administration (or, dispensing that is >0.99 mg/kg body weight)
 - O An extra dose administration within 4 days of the last dose

(The recommended dose for somatrogon is 0.66 mg per kilogram of body weight via a single weekly injection, adjusted by the doctor if necessary.)

For somatropin, the recommended dose in mg per kilogram of body weight via a daily injection, will be manufacturer dependent. Analogous to somatrogon, underdosing and overdosing will be defined as a 50% decrease and increase in dose for a single administration, respectively.

• Long-term efficacy

Where feasible, to evaluate long-term efficacy within the Swedish Growth Hormone Registry database, the following endpoints related to long-term efficacy will be captured:

- o IGF-1 levels
- Height (height velocity (HV), height standard deviation score (SDS), change in height SDS, and final height).

Covariates:

The study will collect all relevant data including patient demographics and clinical characteristics, measured risk factors, co-morbidities, concomitant medications at baseline and co-medications during follow-up to address the study objectives. These data (as available in data sources) will include, but not be limited to:

- Age
- Sex
- Duration of GHD
- Prior medications, including therapies for GHD
- Concomitant medications used at baseline and during follow-up

• Comorbidities: dyslipidemia, reduced bone mineral density, atherogenic risk, thyroid function impairment, neoplasias, intracranial hypertension, intracranial hemorrhage, intracranial aneurysm, type 2 diabetes

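### Section 9.3 states the somatrogon dosing-error limits per dispensing, although 0.33 and 0.99 mg/kg are 50% and 150% of one weekly injection; only secondary descriptive rates are affected

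*Protocol*

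**What the plan says.** Protocol Section 9.3 gives the recommended somatrogon dose as "0.66 mg per kilogram of body weight via a single weekly injection". It then lists four medication-error components.

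- Underdosing: "50% decrease in dose for a single administration (or, dispensing that is <0.33 mg/kg body weight"), and "Missing a dose within the course of 2 weeks".
- Overdosing: "50% increase in dose for a single administration (or, dispensing that is >0.99 mg/kg body weight"), and "An extra dose administration within 4 days of the last dose".

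For somatropin there is no dispensing bracket: "Analogous to somatrogon, underdosing and overdosing will be defined as a 50% decrease and increase in dose for a single administration, respectively".

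Two qualifiers apply. The section opens with "Operational definitions of the following variables will be described in the statistical analysis plan (SAP"), and the component list is introduced by "Where feasible, to evaluate medication errors for somatrogon within the respective databases, utilizing prescription information and weight" measurements.

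Section 9.9 adds the following:

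- None of the four sources records administration, and the injected dose will not be known.
- Doses will be inferred from packaging, prescription frequency and amounts.
- Errors arising from administration at the wrong time are outside what the study can capture.
- Accuracy at single-dose or weekly level is limited. Swedish registry errors are aggregates over 3–6 months.
- A scheduled 15% dose reduction is given as an example of something that would be counted as an error.

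**The concern.** A dispensing is a quantity handed over to cover some period. The limits are amounts for one injection. When a dispensing covers several weeks, dividing its content by body weight and comparing the result with a one-injection limit gives a number that depends mainly on pen size and the child's weight, and hardly on how the child is dosed. Because administration is not observed, the single-administration form of the rule cannot be applied directly, so the bracket is the part a programmer working with dispensing records would reach for.

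Two further items do not fit together. An extra injection within four days can be seen only with injection dates, which no source holds, and it is an error of timing. The 15% example in Section 9.9 does not follow from the 50% rule in Section 9.3.

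At stake are the somatrogon over- and underdosing rates under secondary objective (a).

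**Working it through.** **Inputs.** Recommended dose 0.66 mg/kg weekly and limits 0.33 and 0.99 mg/kg (Section 9.3). Pen contents 24 mg and 60 mg (cover page). The protocol does not give the number of pens or weeks per dispensing, so one pen per dispensing is an assumption. More pens would make the overdose label more frequent and the underdose label rarer.

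**1. Where the limits come from.** 0.66 × 0.5 = 0.33 and 0.66 × 1.5 = 0.99. The stated figures are reproduced exactly, as fractions of one weekly injection.

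**2. Supply of k weeks, limits applied literally.**
- Correct dose: 0.66k > 0.99 when k > 0.99/0.66 = 1.5 weeks. A 4-week supply is 4 × 0.66 = 2.64 mg/kg, labelled overdose.
- Half the recommended dose: 0.33k > 0.99 when k > 3 weeks. A 4-week supply is 1.32 mg/kg, also labelled overdose.

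**3. One pen per dispensing.** Overdose if pen mg / weight > 0.99; underdose if pen mg / weight < 0.33.

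| Pen | Holds more than one weekly dose below | Overdose below | Underdose above |
|---|---|---|---|
| 24 mg | 24/0.66 = 36.4 kg | 24/0.99 = 24.2 kg | 24/0.33 = 72.7 kg |
| 60 mg | 60/0.66 = 90.9 kg | 60/0.99 = 60.6 kg | 60/0.33 = 181.8 kg |

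**4. A 30 kg child with a 60 mg pen.**
- Correct dose: 0.66 × 30 = 19.8 mg a week, so the pen holds 60/19.8 = 3.03 doses. Literal value 60/30 = 2.0 mg/kg: overdose.
- True underdose of 0.30 mg/kg a week (0.30/0.66 = 45% of recommended): 0.30 × 30 = 9 mg a week, so the pen lasts 60/9 = 6.67 weeks if used up. The literal value is again 2.0 mg/kg: overdose.

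The literal rule gives both children the same label. It does not flag everyone: a single 24 mg pen for a 30 kg child is 24/30 = 0.80 mg/kg, inside the limits.

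**5. Dividing by weeks covered.** The two children become 2.0/3 = 0.67 and 2.0/6.67 = 0.30 mg/kg per week, correctly classed if each pen is emptied before refill. If the underdosed child's pen were replaced at 4 weeks (illustrative; the documents give no in-use life), the value is 2.0/4 = 0.50 and the underdose is missed.

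**6. Sensitivity of that measure to refill timing.** For a correct 4-week supply of 2.64 mg/kg, a refill at 6 weeks reads 2.64/6 = 0.44. It is flagged as under only beyond 2.64/0.33 = 8.0 weeks, and as over only before 2.64/0.99 = 2.67 weeks.

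**7. Timing components.** Section 9.3 lists a 4-day extra-dose rule and a 2-week missed-dose rule. Section 9.9 says that no source holds administration records and that the Swedish registry aggregates over 3–6 months. The first rule has no data to work on. The second asks for finer resolution than the registry offers.

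**8. The 15% example.** 0.66 × 0.85 = 0.561 mg/kg, above 0.33, so the 50% rule would not flag it.

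**The case against.** The strongest reply is that nobody would implement the bracket that way. The same line speaks of a single administration, the recommended dose is stated per weekly injection, and the somatropin rule is per administration, so the intended unit is recoverable. Operational definitions are left to the SAP, and Section 9.7 lets the SAP modify the plan. Section 9.9 already bases dose on amounts together with frequency. All of that stands, and it limits the point. It does not make the written unit right: the protocol fixes a number and a unit here, and they do not match. That is a mis-stated rule, not detail left for later.

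Three stronger readings are tempting and not supported.

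- *The problem affects all four countries.* France is excluded for lack of weight data. Spain has no pharmacy dispensing but records prescribed dose and frequency. THIN holds prescription data. The strict dispensing reading bites mainly in Sweden.
- *Section 9.9 expressly contradicts the 4-day rule.* It does not name it. The rule is a timing error of the kind that section excludes, and it needs dates that no source holds, but it sits under a feasibility qualifier. The 3–6-month limit is likewise already disclosed.
- *Dividing by weeks covered recovers the true dose.* Only if each pen is used up before refill (step 5).

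**Conclusion.** The point holds in a limited form. As written, the dispensing limits are per-injection limits on the wrong unit. Under the one-pen assumption a 60 mg pen would be labelled an overdose for any child under 60.6 kg and a 24 mg pen for any child under 24.2 kg, while true underdosing would rarely be detected. The weight cut-offs use only figures in the protocol plus that assumption.

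The consequence arises only if the bracket is carried forward as worded. Even then it touches secondary, descriptive rates collected where feasible and where weight is recorded. Section 9.7 rules out comparative analysis of medication errors, so no primary or comparative result changes. It should be corrected because the correction is cheap and these rates are a stated objective of a safety study committed to the EMA. The 4-day component is not workable with the sources described, the 2-week window cannot be resolved in the Swedish registry, and the 15% example is a minor misstatement. No view is taken on whether 50% is the right threshold.

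**What to change.** In Section 9.3, replace the dispensing bracket with: *prescribed dose per weekly injection or, where only amounts are available, dispensed or prescribed mg / kg / weeks covered, <0.33 or >0.99 mg/kg.* The first form suits Spain; the second suits Sweden and THIN, in each case where weight is recorded. State that the interval form mixes refill timing, missed doses and unused pen content with dose, so some true underdosing will be missed.

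Drop the 4-day extra-dose component. Report missed doses in Sweden only, at the registry's 3–6-month resolution, in place of the 2-week window. In Section 9.9, replace the 15% example with one that crosses the 50% limit, or remove it.

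The cost is wording in two sections and no new data. The price in content is that single-injection errors are no longer claimed outside the source that records prescribed dose, and that the interval measure carries the refill-timing error shown in step 6.
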